DLBC	Lymphoid Neoplasm Diffuse Large B-cell Lymphoma	0.49
GBM	Glioblastoma multiforme	0.46
LIHC	Liver hepatocellular carcinoma	0.46
CHOL	Cholangio carcinoma	0.34
LGG	Brain Lower Grade Glioma	0.3
LAML	Acute Myeloid Leukemia	0.076
THYM	Thymoma	0.047

Abbreviations: PD-1 = programmed death-1; TCGA = The Cancer Genome Atlas; TIGIT = T-cell immunoreceptor with Ig and ITIM domains

Legend: TIGIT and PD1 expression in TCGA. Tumor ranked by R value; tumors with correlation greater than R=.7 are shaded.

The purpose of the study is to determine preliminary clinical activity of this combination in several selected tumor groups and identify which subject characteristics, based on histology, biomarker or prior therapy are most like to benefit from this combination.

This open-label basket study trial design is the most effective to evaluate pan tumor safety and clinical activity by histology, TIGIT, and PD-L1 status.

Subject selected for evaluation in this study all have advanced or metastatic disease, who are not candidates for available, curative standard of care therapies, with cancer types considered as high unmet therapeutic need indications for which limited therapeutic options exist. [Table 1](#) illustrates

the historic objective response rate (ORR) for monotherapy with anti-PD-1/anti-PD-L1 antibodies in the tumor types included in this study.

Table 1 Historical ORR with CPI monotherapy for Treatment Cohorts

Tumor Type	ORR for Single Agent CPI
PD-L1 Positive tumors	
Advanced and/or recurrent or metastatic squamous cell carcinoma of the head and neck or for the first-line treatment of subjects with metastatic or with unresectable, recurrent head and neck squamous cell carcinoma (HNSCC)	14%-18%
Recurrent or metastatic cervical cancer with disease progression on or after chemotherapy whose tumors express PD-L1	14% (Chung et al 2019)
Recurrent locally advanced or metastatic gastric or gastroesophageal junction adenocarcinoma with disease progression on or after 2 or more prior lines of therapy including fluoropyrimidine- and platinum-containing chemotherapy and if appropriate, HER2/neu-targeted therapy.	16%-22%
TMB-H	
Advanced or metastatic TMB-H and MSS solid tumors, that have progressed following prior treatment and who have no satisfactory alternative treatment options.	28%
Independent of PD-L1 Status	

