- Treatment with prior anti-PD-1/anti-PD-L1/2 antibodies is not allowed.

Cohort D

- Histological or cytological evidence of recurrent advanced and/or metastatic **gastric or gastroesophageal junction adenocarcinoma** whose tumors express PD-L1 (CPS >1%), with disease progression on or after 2 or more prior lines of therapy including fluoropyrimidine- and platinum-containing chemotherapy and if appropriate, HER2/neu-targeted therapy.
- Subjects without prior anti-PD-1/anti-PD-L1/2 antibody treatment are eligible.
- Subjects who have received prior anti-PD-1/anti-PD-L1/2 antibodies are eligible provided (i) they have had documented best observed response (BOR) of SD or better in response to an anti-PD1/PD-L1/2 therapy, AND (ii) ≥6 weeks interval since their last dose of prior anti-PD-1/anti-PD-L1/2 treatment

Cohort E

- Histological or cytological evidence of unresectable or metastatic **TMB-H** and **MSS** solid tumors (TMB as defined by an FDA-approved test, e.g., Foundation Medicine >10 mutations/megabase or a Laboratory Developed Test approved by the sponsor (e.g., Guardant Health), that have progressed following prior treatment and who have no satisfactory alternative treatment options. Subjects without prior treatment with anti-PD-1/anti-PD-L1/2 antibody treatment are eligible. Subjects who have received prior anti-PD-1/PD-L1/2 treatment are eligible with at least 6 weeks since their last dose of these prior treatments. Subjects must have had a previous SD or better in response to an anti-PD1/PDL-1/2 therapy. Subjects with the following TMB-H and MSS solid tumors will enroll into the tumor specific cohorts noted below after discussion with the sponsor:

Cohort A: Endometrial cancer PD-1/PD-L1/2 naïve

Cohort C: Cervical carcinoma

Cohort F: Rare tumors (sarcoma, uveal melanoma, germ cell carcinoma)

Cohort H: Ovarian cancer

Cohort F

Rare Tumors

1. Germ Cell Tumors

- Histologically or cytologically confirmed seminoma or non-seminoma testicular **germ cell tumors**.
- Recurrent, advanced and/or metastatic disease, including new lesions, persistently elevated β - human chorionic gonadotropin (HCG) or alpha 1-fetoprotein (AFP) or increase in consecutive elevated serum tumor markers (β -HCG or AFP) done at least one week apart after prior high-dose chemotherapy (HDCT).

Subjects deemed not to be candidates for benefit from potentially curative HDCT may also be eligible including those with:

- (i) inadequate renal function for HDCT

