 - (ii) relapse >2 years after last therapy
 - (iii) inadequate stem cell collection to move forward with HDCT
 - (iv) significant medical or psychosocial comorbidities that are felt to be a contraindication to HDCT by the treating investigator.
- Subjects with serum tumor marker $\geq S2$ HCG and AFP (levels ≥ 1000 for AFP and ≥ 5000 for HCG are excluded).
 - Subjects who have received prior anti-PD1/anti-PD-L1/2 antibodies are excluded.

2. Sarcoma

- Histological diagnosis (with archival or new biopsy sample available for pathology review) of locally advanced/unresectable and/or metastatic soft tissue **sarcoma histopathological subtypes** as noted below, who have radiological evidence of measurable disease and are not candidates for any curative surgery or multimodality therapy:
 - De-differentiated liposarcoma (n=10)
 - Undifferentiated pleomorphic sarcoma (UPS) (n=10)
 - Alveolar soft part sarcoma, malignant peripheral nerve sheath tumors, myxofibrosarcoma (grade 2 or higher), OR pleomorphic dermal sarcoma (total n=5)
- Subjects who have received prior anti-PD-1/anti-PD-L1/2 antibodies as standard of care are excluded.

3. Uveal Melanoma

- Histologically confirmed recurrent **uveal melanoma** with disease progression beyond prior approved standard of care therapy administered in the advanced setting (prior surgical resection of liver metastases, local radiation therapy and adjuvant systemic therapy are acceptable) are eligible.
- Subjects who have received prior anti-PD1/anti-PD-L1/2 antibodies are excluded.

Cohort G

- Histologically confirmed diagnosis of **EC**;
Note: carcinosarcoma (malignant mixed Mullerian tumor), endometrial leiomyosarcoma, and endometrial stromal sarcomas are excluded.
- Subjects must have recurrent, advanced, and/or metastatic disease and must not be candidates for local curative surgery and radiation or intolerant to known standard of care systemic chemotherapy.
- Radiographic evidence of progression after >1 and no more than 3 prior systemic anti-cancer therapy regimens for EC (neoadjuvant, adjuvant, and maintenance treatment are considered part of one treatment line).
- At least 1 measurable target lesion according to RECIST 1.1 that is suitable for repeat measurement including (i) non-nodal lesion that measures ≥ 10 mm in the longest diameter, and (ii) radiographic evidence of subsequent growth after locoregional therapy or EBRT.

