- Prior treatment with any treatment targeting vascular endothelial growth factor (VEGF)-directed angiogenesis, any anti-PD-1, anti-PD-L1/2 agent is allowed.
- Subjects who have received prior anti-PD-1/anti-PD-L1/2 antibodies are also eligible provided (i) they have had documented BOR of SD or better in response to an anti-PD1/PD-L1/2 therapy, AND (ii) ≥ 3 months interval prior to first study drug administration (C1D1) since their last dose of prior anti-PD-1/anti-PD-L1/2 treatment

Cohort H

- Histologically confirmed **high grade serous and endometrioid ovarian cancer, fallopian tube cancer or primary peritoneal cancer**
- Must have received a front-line platinum-based regimen per standard of care after primary or interval debulking surgery and have documented radiological disease recurrence
- Must have measurable disease by RECIST 1.1 as determined by the local investigator/radiology assessment including 2 sites of disease/biopsy accessible disease. Subjects with less than 2 sites will need approval of sponsor prior to enrollment. Note: Maintenance treatment following front-line treatment is permitted and counted together as part of the front-line treatment.
- Subjects who have received prior anti-PD-1/anti-PD-L1/2 antibodies as treatment are excluded.

Subjects are eligible to be included in the study only if the following criteria apply:

2) Prior Therapy

- Radiation therapy must be completed >3 weeks prior to first study drug administration (C1D1). Participants must have recovered from all radiation-related toxicities and/or complications prior to enrollment. Palliative radiotherapy is allowed if completed at least 2 weeks prior to first study drug administration. Subjects must have recovered from all radiation-related toxicities and/or complications prior to enrollment. Subjects must have measurable disease outside the radiation field to be eligible; subjects with progression in a previously radiated field will also be eligible.
- All toxicities attributed to prior anticancer therapy, with the exception of peripheral neuropathy, alopecia, vitiligo, active thyroiditis, and fatigue, must have resolved to Grade 1 (per NCI CTCAE version 5 or higher) or baseline of prior treatment prior to enrollment. Peripheral neuropathy must have resolved to Grade 2 (per NCI CTCAE version 5 or higher).

3) Tumor Specimen

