- a) Prior treatment with CD137 agonists, anti-CTLA-4 and anti-TIGIT antibodies for all cohorts. Any prior anti-PD-1 and anti-PD-L1/2 therapeutic antibodies is excluded for Cohorts A, C, F and H only.
- b) Immune-related AEs that lead to discontinuation of prior immune therapies including anti-PD-1 or anti-PDL-1/2 or anti-CTLA-4 therapies.

- c) Treatment with systemic immunostimulatory agents (including but not limited to IFN α , IL2) within 6 weeks or 5 half-lives of the drug, whichever is shorter, prior to Cycle 1, Day 1.
- d) Systemic anti-cancer chemotherapy, biologic therapy, or other investigational agent within <5 times the half-life of the agent or <28 days (whichever is shorter) of starting study drug with the following exceptions:
 - Hormone-replacement therapy or oral contraceptives.
 - Herbal therapy intended as anti-cancer therapy must be discontinued at least 1 week before Cycle 1, Day 1.
 - Subjects with castrate resistant prostate cancer should be allowed to remain on luteinizing hormone-releasing hormone analogues for medical castration.
 - Previously initiated chronic bisphosphonate or denosumab therapy for bone metastases may be continued during study participation.
- e) Ongoing treatment with chronic immunosuppressants (eg, cyclosporine) or corticosteroids (>10 mg daily prednisone equivalents) or other immunosuppressive medications within 14 days prior to first dose of study drug. Inhaled steroids and adrenal replacement steroid doses >10 mg daily prednisone equivalents are permitted in the absence of active autoimmune disease.
- f) Received oral or IV antibiotics within 2 weeks prior to Cycle 1, Day 1: Subjects receiving prophylactic antibiotics (eg, for prevention of a urinary tract infection or chronic obstructive pulmonary disease) are eligible.
- g) Administration of a live, attenuated vaccine within 4 weeks before Cycle 1, Day 1 or anticipation that such a live attenuated vaccine will be required during the study. Inactivated influenza vaccination is permitted during influenza season only.
- h) History of severe allergic, anaphylactic, or other hypersensitivity reactions to chimeric or humanized antibodies or fusion proteins.

3) Prior Procedures

- a) Major surgical procedure within 28 days prior to Cycle 1, Day 1 or anticipation of need for a major surgical procedure during the course of the study.

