APPENDIX 9: PROTOCOL SYNOPSIS

Name of Sponsor:	Mereo BioPharma 5, INC
Name of Product:	Etigilimab (MPH313) - A humanized immunoglobulin G1 kappa monoclonal antibody
Title of Study:	A Phase 1b/2 Open-Label Study of the Efficacy and Safety of Etigilimab (MPH313) Administered in Combination with Nivolumab to Subjects with Locally Advanced or Metastatic Solid Tumors (ACTIVATE)
Development Phase:	1b/2

Overall Design	
Schematic:	
The diagram illustrates the study's overall design. Cohorts will be enrolled at the discretion of the sponsor. A box on the left lists Key Inclusion Criteria: Age ≥18 years, ECOG 0 or 1, Good Organ Function, Primary endpoint Objective Response Rate (ORR), Secondary Safety and Tolerability, Disease Control Rate (DCR), Duration of Response (DoR), PK/PD, ADA, Exploratory Biomarker, PFS, OS, and a note to review cohort specific inclusion criteria regarding anti-PD-1 / PI-L1 prior therapies. Arrows from these criteria point to eight tumor types: A. Endometrial cancer PD-1 / PD-L1 naïve, B. Head Neck Squamous Cell Carcinoma, C. Cervical carcinoma, D. Gastric cancer or GEJ, E. TMB-H + MSS solid tumors, F. Rare Tumors: Sarcoma, Uveal Melanoma, Germ Cell, G. Endometrial cancer PD-1 / PD-L1 treated, and H. Ovarian cancer. A bracket on the right groups C, D, E, and F as PD-L1 positive.

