10.1.6. Examination of Subgroups

No examination of subgroups will be performed. However all endpoints will be summarised by cohort and, in some instances, by sub-cohorts, or groups of cohorts.

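### Cohort G is labelled post-CPI but its criteria do not require a prior CPI, Cohort E mixes both groups, and no planned summary table separates them

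*Protocol*

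**What the plan says.** - **Purpose.** Protocol 1.4.1 says the study should "identify which subject characteristics, based on histology, biomarker or prior therapy are most like to benefit from this combination". Protocol 1.3 gives TIGIT's suggested part in PD-L1 resistance as the reason for enrolling post-CPI subjects with endometrial, head and neck, and TMB-high/MSS tumours.
- **Cohort G, label.** The schema in the synopsis (Appendix 9) reads "G. Endometrial cancer PD-1 / PD-L1 treated". SAP 10.1.2 calls the cohort EC Post-CPI, and the table shells in SAP section 14 head its column Post-CPI.
- **Cohort G, criteria (Protocol 3.1, repeated in the synopsis).** Entry rests on "Radiographic evidence of progression after >1 and no more than 3 prior systemic anti-cancer therapy regimens for EC". Of prior treatment it says "any anti-PD-1, anti-PD-L1/2 agent is allowed", and then "Subjects who have received prior anti-PD-1/anti-PD-L1/2 antibodies are also eligible provided (i) they have had documented BOR of SD or better". Exclusion 2a in Protocol 3.2 adds "Any prior anti-PD-1 and anti-PD-L1/2 therapeutic antibodies is excluded for Cohorts A, C, F and H only".
- **Cohort E, criteria.** "Subjects without prior treatment with anti-PD-1/anti-PD-L1/2 antibody treatment are eligible"; pretreated subjects may also enter, given a minimum interval and an earlier SD or better.
- **Analysis.** SAP 10.1.6 states "No examination of subgroups will be performed", with an exception for cohorts, sub-cohorts and groups of cohorts. The only sub-cohorts named in SAP 10.1.2 are tumour types within Cohort F. Table 14.2.1 has a single column each for E and G.
- **Data held.** Listing 16.2.4.4.2 shows, per subject, the last dose of and best response to a prior PD-1/PD-L1 inhibitor. Listing 16.2.6.4.1 shows each subject's best overall response.

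**The concern.** The label tells the reader that every subject in the Cohort G column has already had a checkpoint inhibitor. The criteria do not guarantee that. A response in a naive subject may owe nothing to overcoming resistance, since nivolumab is half of the regimen and Table 1 credits single-agent CPI with 23%–40% ORR in endometrial carcinoma. Under the label, that response would be read as activity after CPI.

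In Cohort E the mixture is declared, but one pooled ORR describes neither population. These two cohorts carry the post-CPI efficacy question alone: the footnotes to Table 14.2.1 say that nobody was recruited to Cohort D and that Cohort B has no response-evaluable subjects.

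**Working it through.** **1. Does any Cohort G criterion require a prior CPI?** Prior anti-PD-1/PD-L1 is allowed. Pretreated subjects are *also* eligible, which presupposes that others qualify. None of the two or three prior regimens has to be a CPI. Exclusion 2a bars pretreated subjects from A, C, F and H, but nothing bars naive subjects from G. The labels and the criteria therefore disagree.

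**2. Where would a naive endometrial subject with two or three regimens go?** Cohort A takes progression after one platinum regimen, with one more allowed only if neoadjuvant or adjuvant. Such a subject generally falls outside A and inside G.

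**3. Does any planned summary separate the groups?** Table 14.2.1 does not. Table 14.1.4.1 counts prior biologic or immunotherapy yes/no, which does not isolate PD-1/PD-L1 agents. The sub-cohort exception names only Cohort F tumour types. The listings allow a hand count but no planned table does it.

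**4. How much could mixing matter?** The plan gives no figure for this. Its two-stage error rates (Type 1: 0.0468 and 80.11%; Type 2: 0.0471 and 80.51%) reproduce exactly, but they assume one response rate per cohort and are not used here.

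Inputs: naive ORR p_n = 23% or 40% (Table 1, endometrial; not split by prior CPI). Post-CPI ORR p_c = 5% and the number of naive subjects k among 10 are assumptions.

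Expected ORR = [k·p_n + (10 − k)·p_c] / 10. Share of expected responses from naive subjects = k·p_n / [k·p_n + (10 − k)·p_c].

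| k of 10 | Expected ORR, p_n 23% | Expected ORR, p_n 40% | Naive share of responses |
|---|---|---|---|
| 0 | 5.0% | 5.0% | 0% |
| 1 | (0.23 + 0.45)/10 = 6.8% | (0.40 + 0.45)/10 = 8.5% | 34%–47% |
| 2 | (0.46 + 0.40)/10 = 8.6% | (0.80 + 0.40)/10 = 12.0% | 53%–67% |
| 5 | (1.15 + 0.25)/10 = 14.0% | (2.00 + 0.25)/10 = 22.5% | 82%–89% |

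If p_c is 10% instead, k = 2 gives (0.46 + 0.80)/10 = 12.6% to (0.80 + 0.80)/10 = 16.0%, with a naive share of 37%–50%.

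For Cohort E, taking Table 1's 28% for naive subjects, 5% after CPI and an even split (the last two assumed), the pooled rate is (0.28 + 0.05)/2 = 16.5%, far from both components.

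**5. How precise would a split be?** With 0 responders among n, the upper Clopper-Pearson 95% limit is 1 − 0.025^(1/n): 52.2% for n = 5, 30.8% for n = 10, 16.8% for n = 20.

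**The case against.** The strongest reply is that the data are all there. Prior CPI and best response are both listed per subject, so anyone with the listings can tabulate one against the other. That stands. A reader might infer that the trial cannot show whether the combination works after a CPI; the documents do not support that. What is missing is a summary display.

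Second, contamination of Cohort G is hypothetical. The schema shows the intent, the sponsor approves each enrolment form (Protocol 8), and nothing says that a naive subject entered. That also stands. If none did, the G column is a valid, if small, post-CPI estimate.

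Third, one might carry the illustration through to the 29-subject Simon rule and speak of an inflated error rate. That does not apply. SAP 6.3 records the stage 1 evaluation only for the cervical and uveal cohorts, so G reached no Simon decision before termination. The figure assigning cohorts to design types is not available in the text, and the result depends heavily on the type. SAP 10.1.3 plans no formal testing.

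Fourth, prior therapy appears in the design and rationale text, not in the objectives table (Protocol 2), and Cohort E's mixture is open. This lowers the weight of the point, but a stated purpose still deserves a table. One sentence in Cohort E, requiring earlier SD or better on anti-PD-1/PD-L1, carries no explicit limit to pretreated subjects. The text just before it admits naive subjects, so it can sensibly apply only to the pretreated.

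**Conclusion.** The point holds as a mismatch of label and criteria plus a gap in the summary outputs. Cohort G's criteria would admit a CPI-naive subject whom the SAP would report as post-CPI; Cohort E is mixed by design; and one ORR per cohort leaves post-CPI activity unsummarised.

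The size in G is unknown and may be nil. On the assumptions above, two naive subjects in ten would lift the expected ORR from 5% to 8.6%–12.0% and account for over half of expected responses. The mixing in E does not depend on what happened in G. Nothing here undermines the pooled ORR as a description of the subjects enrolled. The fault lies in reading it as a post-CPI result.

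**What to change.** 1. Reconcile the Cohort G criteria (Protocol 3.1 and synopsis) with the synopsis schema and the SAP 10.1.2 label, and record which reading governed enrolment. In outputs, use Post-CPI only for subjects with documented prior anti-PD-1/PD-L1.
2. Add prior anti-PD-1/PD-L1 yes/no counts to Table 14.1.4.1, by cohort. If G proves wholly pretreated, this confirms the label.
3. In SAP 10.8.1.1, 10.8.2.1 and Table 14.2.1, show ORR and DCR within Cohorts E and G by prior CPI (yes/no), with n/N and Clopper-Pearson intervals. Name this as a sub-cohort display under SAP 10.1.6 so that the two sections agree.

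The cost is SAP wording, some extra rows and columns, and programming from data already collected. The drawback is small denominators: with 0 of 10 responders the interval still reaches 31%, so the split should be presented as descriptive only.

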3.2. Exclusion Criteria

Subjects are excluded from the study if any of the following criteria apply:

1) Medical Conditions

- Severe allergic or anaphylactic reaction to any monoclonal antibody therapy, murine protein, or known hypersensitivity to any excipient in the study drugs.
- Major surgery within 4 weeks prior to screening.
- Subjects who have received radiotherapy within <1 week of starting study treatment, or who have unresolved associated AEs.
- Following known active viral infections:
 - Known HIV infection.
 - Active hepatitis B or hepatitis C infection at the time of screening for the study. Active hepatitis B is defined as a known positive hepatitis B surface antigen (HBsAg) result. Active hepatitis C is defined as a known positive hepatitis C antibody result and known quantitative HCV RNA results greater than the lower limit of detection of the assay.
 - Subjects with past hepatitis B virus (HBV) infection or resolved HBV infection (defined as the presence of hepatitis B core antibody and absence of HBsAg) are eligible. HBV DNA must be obtained in these subjects prior to randomization. Subjects with positive hepatitis B serology who are immune due to vaccination, resolved wild-type infection or passive immunization due to immunoglobulin therapy will be eligible.
 - Subjects with past hepatitis C (HCV) infection and positive for HCV antibody are eligible only if PCR is negative for HCV RNA.
 - History of active non-infectious pneumonitis or history of pneumonitis that required steroids or current pneumonitis.
- Ongoing systemic bacterial, fungal, or viral infections at screening.
 - NOTE: Subjects on antimicrobial, antifungal, or antiviral prophylaxis are not specifically excluded if all other inclusion/exclusion criteria are met.
- Female subjects who are pregnant or breastfeeding. Serum pregnancy test (for women of childbearing potential, including women who have had a tubal ligation) must be performed and documented as negative within 7 days prior to Cycle 1 Day 1.

- g) Concurrent active malignancy other than non-melanoma skin cancer, carcinoma in situ of the cervix, or prostate intraepithelial neoplasia.
- h) Subjects with active, known, or suspected autoimmune disease. Subjects with vitiligo, type I diabetes mellitus, residual hypothyroidism due to autoimmune condition only requiring hormone replacement, psoriasis not requiring systemic treatment, or conditions not expected to recur in the absence of an external trigger are permitted to enroll. Subjects with minor autoimmune disease after discussion with the Medical Monitor.
- i) History of stroke, unstable angina, myocardial infarction, or ventricular arrhythmia requiring medication or mechanical control within the last 6 months prior to screening.
- j) Unstable or severe uncontrolled medical condition (eg, unstable cardiac function, unstable pulmonary condition including pneumonitis and/or interstitial lung disease, uncontrolled diabetes) or any important medical illness or abnormal laboratory finding that would, in the investigator's judgment, increase the risk to the subject associated with his or her participation in the study.
- k) History of any Grade 3 or 4 immune-related AE toxicity from prior immunotherapy that resulted in treatment discontinuation.
- l) Has primary central nervous system (CNS) malignancy or known untreated/active CNS metastases and/or carcinomatous meningitis.
 - Subjects with previously treated, asymptomatic brain metastases may participate provided they meet the following criteria: clinically stable for at least 4 weeks and have no evidence of new or enlarging brain metastases and are off steroids 14 days prior to dosing with study medication. Stable brain metastases by this definition should be established prior to the first dose of study drug.
 - Subjects with asymptomatic brain metastases (ie, no neurological symptoms, no requirements for corticosteroids, and no lesion >1.5 cm) may participate but will require regular imaging of the brain as a site of disease.
 - Subjects with CNS symptoms should undergo a computed tomography (CT) scan or magnetic resonance imaging (MRI) of the brain to exclude new or progressive brain metastases. Spinal cord metastasis is acceptable. However, subjects with spinal cord compression must be excluded.
- m) Medical psychological or social conditions that may interfere with the subject's participation in the trial or evaluation of trial results

2) Prior Therapy

- a) Prior treatment with CD137 agonists, anti-CTLA-4 and anti-TIGIT antibodies for all cohorts. Any prior anti-PD-1 and anti-PD-L1/2 therapeutic antibodies is excluded for Cohorts A, C, F and H only.
- b) Immune-related AEs that lead to discontinuation of prior immune therapies including anti-PD-1 or anti-PDL-1/2 or anti-CTLA-4 therapies.

- c) Treatment with systemic immunostimulatory agents (including but not limited to IFN α , IL2) within 6 weeks or 5 half-lives of the drug, whichever is shorter, prior to Cycle 1, Day 1.
- d) Systemic anti-cancer chemotherapy, biologic therapy, or other investigational agent within <5 times the half-life of the agent or <28 days (whichever is shorter) of starting study drug with the following exceptions:
 - Hormone-replacement therapy or oral contraceptives.
 - Herbal therapy intended as anti-cancer therapy must be discontinued at least 1 week before Cycle 1, Day 1.
 - Subjects with castrate resistant prostate cancer should be allowed to remain on luteinizing hormone-releasing hormone analogues for medical castration.
 - Previously initiated chronic bisphosphonate or denosumab therapy for bone metastases may be continued during study participation.
- e) Ongoing treatment with chronic immunosuppressants (eg, cyclosporine) or corticosteroids (>10 mg daily prednisone equivalents) or other immunosuppressive medications within 14 days prior to first dose of study drug. Inhaled steroids and adrenal replacement steroid doses >10 mg daily prednisone equivalents are permitted in the absence of active autoimmune disease.
- f) Received oral or IV antibiotics within 2 weeks prior to Cycle 1, Day 1: Subjects receiving prophylactic antibiotics (eg, for prevention of a urinary tract infection or chronic obstructive pulmonary disease) are eligible.
- g) Administration of a live, attenuated vaccine within 4 weeks before Cycle 1, Day 1 or anticipation that such a live attenuated vaccine will be required during the study. Inactivated influenza vaccination is permitted during influenza season only.
- h) History of severe allergic, anaphylactic, or other hypersensitivity reactions to chimeric or humanized antibodies or fusion proteins.

3) Prior Procedures

- a) Major surgical procedure within 28 days prior to Cycle 1, Day 1 or anticipation of need for a major surgical procedure during the course of the study.
- b) Subjects who received investigational (not authorized or approved by relevant Health Authorities) COVID-19 vaccine or therapies prior to screening are not eligible without discussion with sponsor.
- c) History of additional prior malignancy with the exception of cured skin, bladder, prostate, cervical, or other carcinoma in situ with no evidence of active disease for at least 1 year.

